2.1.2 Exclusion Criteria

2.1.2.1 Patients who have had standard of care chemotherapy, large field radiotherapy, or major surgery must wait 2 weeks prior to entering the study. For recent experimental therapies a 28 day period of time must elapse before treatment.

2.1.2.2 Patients who have undergone prior liver transplantation are ineligible.

2.1.2.3 Patients with known brain metastases will be excluded from this clinical trial because of their poor prognosis and because they often develop progressive neurologic dysfunction that would confound the evaluation of neurologic and other adverse events.

2.1.2.4 Uncontrolled intercurrent illness including, but not limited to, ongoing or active systemic infection, symptomatic congestive heart failure, unstable angina pectoris, cardiac arrhythmia (excluding insignificant sinus bradycardia and sinus tachycardia) or psychiatric illness/social situations that would limit compliance with study requirements.

2.1.2.5 History of chronic autoimmune disease (e.g., Addison's disease, multiple sclerosis, Graves' disease, Hashimoto's thyroiditis, rheumatoid arthritis, hypophysitis, etc.) with symptomatic disease within the 3 years before randomization. Note: Active vitiligo or a history of vitiligo will not be a basis for exclusion.

- 2.1.2.6 Dementia or significantly altered mental status that would prohibit the understanding or rendering of Information and Consent and compliance with the requirements of the protocol.
- 2.1.2.7 Diverticulitis (either active or history of) within the past 2 years. Note that diverticulosis is permitted.
- 2.1.2.8 Active or history of inflammatory bowel disease (colitis, Crohn's), irritable bowel disease, celiac disease, or other serious, chronic, gastrointestinal conditions associated with diarrhea. Active or history of systemic lupus erythematosus or Wegener's granulomatosis.
- 2.1.2.9 Currently receiving immunosuppressive doses of steroids or other immunosuppressive medications (inhaled and topical steroids are permitted)
- 2.1.2.10 History of sarcoidosis syndrome
- 2.1.2.11 Patients should not be vaccinated with live attenuated vaccines within 1 month of starting Tremelimumab treatment.
- 2.1.2.12 Has a known history of Human Immunodeficiency Virus (HIV) (HIV 1/2 antibodies)
- 2.1.2.13 HIV-positive patients receiving anti-retroviral therapy are excluded from this study due to the possibility of pharmacokinetic interactions between antiretroviral medications and Tremelimumab. HIV positive patients not receiving antiretroviral therapy are excluded due to the possibility that Tremelimumab may worsen their condition and the likelihood that the underlying condition may obscure the attribution of adverse events.
- 2.1.2.14 History of hypersensitivity reaction to human or mouse antibody products.
- 2.1.2.15 Pregnancy and breast feeding are exclusion factors. The effects of Tremelimumab on the developing human fetus are unknown. Enrolled patients must agree to use adequate contraception (hormonal or barrier method of birth control; abstinence) prior to study entry, the duration of study participation and 3 months after the end of the treatment. Should a woman become pregnant or suspect she is pregnant while she or her partner is participating in this study, she should inform her treating physician immediately.
- 2.1.2.16 Patients with unhealed surgical wounds for more than 30 days.
- 2.1.3 Re-Induction Criteria (if applicable)
 - 2.1.3.1 Subjects must have entered the Maintenance Phase and are under ongoing maintenance treatment
 - or** Subjects who stopped maintenance treatment because of a CR
 - or** Subjects with an initial PR or CR or at least 3 months of SD on tumor assessment
 - and** who subsequently have a confirmed and documented disease progression (per immune-related RECIST criteria).
 - 2.1.3.2 Patients are excluded from re-induction if they have experienced any related Dose-limiting toxicities as described in Section 3.6, delayed dosing beyond 35 days due to Tremelimumab-related AEs, or have been taken off treatment due to toxicity as described in Section 3.8.3.

2.1.3.3 Patients who have progressed on initial therapy will not be considered for re-induction treatment.

2.1.3.4 Tremelimumab Dose: Patients will be treated at the same dose of Tremelimumab as they previously received. For patients on Dose Level 1 who had already satisfied criteria for escalation to 10mg/kg they will be re-treated at 10mg/kg.

2.1.3.5 The patient must – at the time of re-induction – satisfy all the eligibility criteria as set out in Sections **2.1.1** & **2.1.2**.

2.1.3.6 The patient must be discussed at GI Tumor Board, NCI and suitability for the interventional procedure (TACE or RFA) re-affirmed.

Eligible patients will follow the same treatment criteria, evaluation plan and schedule as was previously described for the main part of the study, and doses may be delayed or modified as described in Section **3.8**. There will be no limit to the number of additional re-inductions a patient may receive if the same efficacy and safety criteria described above are met, until intolerable toxicity or progressive disease necessitates ending the re-induction phase.

2.1.4 Inclusion of Women and Minorities

Men and women of all races and ethnic groups are eligible for this trial.

2.1.5 Recruitment Strategies

The study will be posted on the CCR website and on clinicaltrials.gov.

2.2 SCREENING EVALUATION

2.2.1 History and Physical Examination

Complete history (including prior hormone use) and physical examination (including height, weight, vital signs, EKG, and performance status) will be conducted prior to starting study drug.

2.2.2 Laboratory Evaluation

- Hematological profile: CBC with differential and platelet count, PT, INR, aPTT, fibrinogen.
- Biochemical profile: electrolytes, BUN, creatinine, AST, ALT, total bilirubin (including direct and indirect), calcium, phosphorus, albumin, magnesium, uric acid, amylase.
- Serum or urine pregnancy test for female participants of childbearing age (in the absence of prior hysterectomy). Test to be performed within 72 hours prior to initiating treatment.

2.2.3 Histologic confirmation (at any time point prior to commencement)

A block or unstained slides of primary or metastatic tumor tissue will be required from each participant to confirm diagnosis with analysis being performed by the Laboratory of Pathology, NIH. As stated in the inclusion criteria above, histopathological confirmation of carcinoma may be sufficient. Fibrolammellar variant is also allowed.

2.3 BASELINE STUDIES

2.3.1 Imaging studies (obtained within 28 days prior to first dose)

- CT scan of chest, abdomen and pelvis
And/or
- MRI liver

2.3.2 Laboratory evaluation (obtained within 72 hours prior to first dose)

If laboratory tests are done within 72 hours of Cycle 1 Day 1 they do not need to be repeated on Day 1.

- Hematological profile: CBC with differential and platelet count, PT, INR, aPTT, fibrinogen.
- Biochemical profile: electrolytes, BUN, creatinine, AST, ALT, total bilirubin (including direct and indirect), calcium, phosphorus, albumin, magnesium, uric acid, amylase.
- Tumor marker profile: aFP or Ca19.9 (obtained within 7 days prior to first dose)

2.3.3 Laboratory evaluation (obtained within 28 days prior to first dose)

- Thyroid function tests (TSH, T3, T4)
- Hepatitis B and/or C viral load and serology
- HLA-A2 phenotype

2.3.4 History and physical exam with vital signs (obtained within 1 week prior to first dose).

2.3.5 Electrocardiogram (obtained within 28 days prior to first dose)

2.4 REGISTRATION PROCEDURES

Authorized staff must register an eligible candidate with NCI Central Registration Office (CRO) within 24 hours of signing consent. A registration Eligibility Checklist from the web site (<http://home.ccr.cancer.gov/intra/eligibility/welcome.htm>) must be completed and sent via encrypted email to: NCI Central Registration Office [contact]. After confirmation of eligibility at Central Registration Office, CRO staff will call pharmacy to advise them of the acceptance of the patient on the protocol prior to the release of any investigational agents. Verification of Registration will be forwarded electronically via e-mail to the research team. A recorder is available during non-working hours.

3 STUDY IMPLEMENTATION

3.1 STUDY DESIGN

- The proposed study is a pilot study of Tremelimumab - at a planned dose 10mg/kg/IV q 4 weekly - in patients with advanced HCC treated with either TACE or RFA.

The initial study population is Cohort A as described below and these patients will be treated with either RFA or TACE. The decision on which treatment to administer (i.e. RFA vs. TACE) will be made in consultation with the interventional radiologists. The reason for this is that there are technical considerations (size and location of lesion, main portal vein occlusion etc.) which would make one procedure preferable over the other.

Cohort	Population	Immune stimulative procedure	Dose level (Trem)	Planned N
A	Advanced HCC, BCLC Stage C	RFA/TACE	3.5mg/kg	3-6
			10mg/kg	20
B	Intermediate HCC, BCLC B	TACE	10mg/kg	20

- Transarterial chemoembolization is percutaneous procedure performed under general anesthesia or conscious sedation. (See 3.9.1 for details)
- Patients undergoing trans-arterial chemoembolization, RFA or cryoablation are pre-medicated with analgesics, antibiotics and anti-emetics per clinical standards. For details regarding each procedure please see 3.9.
- We will also enroll an additional cohort of N=20 patients (Cohort B) with liver-confined disease for whom TACE is indicated as standard of care. These patients will receive TACE in combination with Tremelimumab using the same schema, although for these patients TACE may be repeated (as per standard of care). They will not receive RFA.
- With protocol amendment F, it was proposed that once cohort A has demonstrated safety and feasibility for the combination of ablative treatment and tremelimumab in HCC, we will add 3 additional cohorts (C-E) to the study. However, with amendment I we have revised the study design to remove Cohort C, so only 2 cohorts, D and E, remain. For these cohorts, the schedule of administration for tremelimumab and the timing of the immune-stimulative procedure is identical to cohorts A and B, as summarized below.

Cohort	Population	Immune stimulative procedure	Dose level (Trem)	Planned N
D	Advanced HCC, BCLC Stage C	Cryoablation	10mg/kg	10

E	Intrahepatic cholangiocarcinoma	RFA	10mg/kg	20
---	------------------------------------	-----	---------	----

3.2 SCHEDULE

- Day 1: Tremelimumab IV every 4 weeks x 6 doses and then every 12 weeks for 2 years or until disease progression whichever comes first.
- Day 36 [+/- 96 hours]: RFA or TACE.
- Restaging CT /MRI scan every 8 weeks to evaluate TTP in target lesion. (Both standard RECIST and Immune-related Response Criteria [irRC] will be employed).
- Dose: (Cohort A only): Initially three to six patients will be treated at 3.5mg/kg (with subsequent dosing also at 3.5mg/kg) prior to enrolling to the 10mg/kg dose level. If a single patient experiences dose-limiting toxicity (DLT) related to the combination this cohort will be expanded to N=6 as per a standard 3+3 design. If 3.5mg/kg is established to be safe we will proceed to the 10mg/kg dose level. N=20 patients in cohort A will be treated at 10mg/kg.
- For Cohort A (BCLC Stage C patients): TACE or radiofrequency ablation (RFA) will be performed once only.
- For Cohort B (BCLC Stage B patients): TACE may be repeated (as per standard of care) on months 3, 7, and 13, and q6 months thereafter (if indicated).
- Cohort B will only be recruited following completion of the dose-escalation portion of Cohort A.

For Cohort E (BTC patients, status post prior chemotherapy with intrahepatic disease) RFA will be performed once only, also on Day 36 (+/- 96hrs).

3.3 COHORT A

3.3.1 Definition

The definition of Cohort A is as follows:

Cohort A (N=23-26):

- Advanced stage HCC, BCLC group C
- Patients must have progressed on, been intolerant of prior sorafenib therapy.
- Child Pugh A/B7
- No available surgical option (i.e. transplantation or hepatic resection) or curative ablative option.
- Disease amenable to either TACE or RFA

3.3.2 Treatment

Three patients will be treated at 3.5mg/kg (with subsequent dosing also at 3.5mg/kg i.e. no inpatient dose escalation) prior to enrolling to the 10 mg/kg dose level. If a single patient experiences dose-limiting toxicity (DLT) related to the combination of TACE/RFA and

Tremelimumab this cohort will be expanded to N=6 as per a standard 3+3 design. If 3.5mg/kg is established to be safe we will proceed to the 10 mg/kg dose level. N=20 patients will be treated at 10 mg/kg to evaluate the feasibility endpoint, provided no more than 2 of 3-6 patients have a DLT at this level.

Dose level	Tremelimumab dose (mg/kg)	N
1	3.5	3-6
2	10	20

- The 3.5 mg/kg cohort will have at least 3 patients to evaluate for toxicity to establish MTD for the combination of Tremelimumab with either TACE or RFA. Three patients will be treated at this dose level. The descriptions and grading scales found in the revised NCI Common Terminology Criteria for Adverse Events (CTCAE) version 4.0 will be utilized for AE reporting. If none of the three patients at the 3.5 mg/kg dose level experiences dose-limiting toxicity (DLT), accrual to DL2 will proceed to the 10mg/kg cohort. If one of three patients treated at a dose level experiences DLT that is considered to be at least possibly related to the combination of Tremelimumab with either TACE or RFA, then three more patients will be enrolled at that same level. If the incidence of DLT among those six patients is one in six, then we will proceed to 10 mg/kg. If two or more of the six patients experience DLT, then the MTD is considered to have been exceeded.
- Evaluation period for Dose-limiting Toxicities (DLT) will extend for the first 8 weeks of the study.
- Following completion of the dose escalation portion of the study Tremelimumab will be administered at the MTD at the same schedule. A total of 20 patients will be treated in cohort A at the MTD, not including those patients treated at the lower doses.
- For patients on Dose Level 1 who have completed at least 16 weeks of protocol therapy, we will consider dose escalation to 10mg/kg if criteria for continuance of therapy are met and the patient does not have >Grade 2 toxicity attributable to tremelimumab.

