3.3.3 Protocol Stopping Rules

This study will utilize the Common Terminology Criteria for Adverse Events (CTCAE) version 4.0 for grading systemic toxicity. For safety reasons, the protocol will be temporarily halted pending discussions with the NCI IRB and Sponsor regarding necessary amendment for either of the following events:

- One occurrence of grade 5 toxicity by the NCI-CTCAE version 4.0 attributable to the treatment regimen.
- Two occurrences of grade 4 toxicity by the NCI-CTCAE version 4.0 attributable to the treatment regimen.

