3.4.2 Treatment

The treatment schema for both cohorts is identical with the exception of the fact that in cohort B TACE may be repeated (as per standard of care) on months 3, 7, and 13, and q6 months thereafter (if indicated).

Patients in Cohort B will only be recruited following completion of the dose-escalation portion of Cohort A and will be treated at the dose level which has been determined to be safe in that cohort.

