3.6 COHORTS D-E

Once safety is established for the initial concept of combining anti-CTLA4 with ablative procedures (RFA and TACE), we will similarly explore feasibility of tremelimumab at the same dose and schedule in 2 additional cohorts (denoted D-E) evaluating tremelimumab in

combination with cryoablation in HCC (cohort D) and with RFA in a cohort of patients with biliary tract carcinoma (cohort E).

- For these additional cohorts, the dose (10mg/kg) and schedule of tremelimumab will be as per cohorts A and B. The timing of the interventional procedure will also be identical.
- Cohort Definition: Cohort D will have the same definition as Cohort A above:
Advanced stage HCC, BCLC group C
Patients must have progressed on, been intolerant of prior sorafenib therapy.
Child Pugh A/B7
No available surgical option (i.e. transplantation or hepatic resection) or curative ablative option.
Disease amenable to cryoablation
- Cohort E will contain BTC patients as specified in the eligibility criteria.
- For cohorts D-E no dose escalation will occur. All patients will receive tremelimumab at 10mg/kg at the same schedule established as safe and feasible in Cohort A of the study. However, protocol stopping rules will apply as outlined in Section 3.3.

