3.7 DOSE LIMITING TOXICITIES

3.7.1 Definition of Dose-limiting Toxicities (DLTs):

A DLT is defined as a \geq Grade 3 adverse drug reaction (ADR) according to the NCI-CTCAE v4.0, that is possibly, probably, or definitely related to the combination of Tremelimumab with either TACE or RFA, occurring during the DLT evaluation period except for any of the following outlined in section 3.6.2. ADRs are defined in this trial as any AEs suspected to be related to Tremelimumab by the investigator. Evaluation period for Dose-limiting Toxicities (DLT) will extend for the first 8 weeks of the study.

Treatment-related SAE will be ascribed as related to drug except where a clear relationship to the underlying disease or recognized co-morbidities is evident. For this trial, the MTD is defined as the highest dose where < 2 of 6 subjects experience a DLT.

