8.1 COHORTS A AND B

Relative to the feasibility endpoint, this will be decided in Cohorts A and B; all patients enrolled into Cohorts A and B at the 10 mg/kg dose level will be considered as one group for feasibility evaluation. Feasibility will be evaluated in the first 20 evaluable patients enrolled in in these two cohorts on this trial at the 10mg/kg dose level following a dose-escalation phase of 3-6 patients treated at 3.5mg/kg dose level. The safety of the 10 mg/kg dose level will be evaluated in the first 3-6 patients treated at that dose. If there are 2 or more DLTs among the first 3-6 patients treated at this level, then accrual would stop. Regarding feasibility, it would be desirable if the fraction of patients who could receive three doses of the monoclonal antibody were consistent with 80% or higher and greater than 50%. With 20 evaluable patients, if there are 14 or more patients who are able to receive three doses of the monoclonal antibody, then there is a 5.8% probability of this being true if the true probability of an individual patient being able to receive this much antibody were 50% and there is a 91.3% probability of this being true if the true probability for an individual were 80%. Thus, 14 or more out of 20 patients receiving three doses of antibody would provide strong evidence that it is feasible to administer this antibody in a substantial fraction of patients, consistent with 80% or more and this would be considered a successful outcome for the trial.

Prior to amendment G, administration of three doses has been determined to be feasible based on the first 20 total patients enrolled and the feasibility evaluation was considered to have ended at that point. Evaluations for clinical efficacy will be the primary objective from this point forward.

With amendment G, there will be 20 patients enrolled in cohort A at 10mg/kg (10 receiving RFA and 10 receiving TACE).

Each of these sub-cohorts will be evaluated for efficacy as follows. In each sub-cohort of 10 patients the trial will have 82% power to rule out 15% 6 month as the proportion stable at 6

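### Section 3.3.2 lets accrual at 10 mg/kg continue with exactly 2 DLTs; section 8.1 stops it at 2, and the MTD definition agrees with 8.1

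*Combined protocol and SAP*

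**What the plan says.** Section 3.3.2 sets the condition for treating 20 Cohort A patients at 10 mg/kg: "provided no more than 2 of 3-6 patients have a DLT at this level".

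Section 8.1 covers the same dose and the same patients: "If there are 2 or more DLTs among the first 3-6 patients treated at this level, then accrual would stop".

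Three other statements bear on which limit is meant:

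- Section 3.7.1 says that "the MTD is defined as the highest dose where" fewer than 2 of 6 subjects have a DLT.
- A bullet in 3.3.2 says the MTD has been exceeded once two or more of six patients have a DLT. The bullet opens with the 3.5 mg/kg level, but its expansion step is worded for any dose level.
- Another bullet in 3.3.2 says "A total of 20 patients will be treated in cohort A at the MTD".

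Later cohorts rest on the outcome. Cohort B patients "will be treated at the dose level which has been determined to be safe in that cohort" (3.4.2). For Cohorts D-E, section 3.6 says: "All patients will receive tremelimumab at 10mg/kg at the same schedule established as safe and feasible in Cohort A of the study".

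**The concern.** One safety decision has two written rules that give opposite answers for one possible result. With exactly 2 DLTs among the first 3-6 patients at 10 mg/kg, 3.3.2 permits accrual to 20 and 8.1 closes it. Someone working from the treatment section and someone working from the statistical section could each follow the protocol and act differently.

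Safety is part of the primary objective (1.1.1), and Cohorts D-E have no dose escalation of their own. What it means to say that 10 mg/kg was shown to be safe in Cohort A therefore depends on which count was applied. The documents do not report the number of DLTs seen at that dose, so a reader cannot tell whether the stricter rule was met.

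**Working it through.** **Step 1: compare the rules by DLT count in the first 3-6 patients at 10 mg/kg.**

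| DLTs | 3.3.2 clause | 8.1 | 3.7.1 definition (of 6) |
|---|---|---|---|
| 0 or 1 | continue | continue | can be the MTD |
| exactly 2 | continue | stop | cannot be the MTD |
| 3 or more | stop | stop | cannot be the MTD |

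The conflict is confined to the middle row.

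**Step 2: decide which clause is wrong.** Under 3.7.1 a dose with 2 of 6 DLTs is not the MTD, yet 3.3.2 says the 20 patients are treated at the MTD. The 3.3.2 bullet on two or more of six, and the description of the design as a standard 3+3, point the same way. Only the one clause in 3.3.2 allows 2.

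**Step 3: check whether another rule closes the gap.** The halt in 3.3.3 needs one attributable grade 5 event or "Two occurrences of grade 4 toxicity by the NCI-CTCAE version 4.0 attributable to the treatment regimen". Under 3.7.1 a DLT can be grade 3. Two grade 3 DLTs, or one grade 3 and one grade 4, therefore trigger no halt.

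**Step 4: size the difference.** The plan gives no operating characteristics for the DLT rule, so there is no stated figure to reproduce. It gives no DLT rate either, so the true rates p below are assumptions. The 27% row uses the grade 3-4 adverse event rate quoted in 1.2.5 for 10 mg/kg every 4 weeks in melanoma. It is a reference point, not a DLT rate.

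Let b0, b1 and b2 be the Binomial(3, p) probabilities of 0, 1 and 2 DLTs in three patients: b0 = (1-p)^3, b1 = 3p(1-p)^2, b2 = 3p^2(1-p). The probability of continuing at 10 mg/kg is:

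- A. Stop at 2 (8.1): b0 + b1·b0
- B. 2 of 6 may continue, reached through 1 of the first 3: b0 + b1·(b0 + b1)
- C. As B, and 2 of the first 3 also expands to six with a cap of 2: B + b2·b0
- D. As B, and 2 of 3 passes outright: B + b2

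B is the natural reading of the 3.3.2 clause inside a 3+3. C and D are more permissive and less likely readings, possible because the clause does not say what follows 2 DLTs in the first three.

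Worked at p = 0.20: b0 = 0.512, b1 = 0.384, b2 = 0.096.

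- A = 0.512 + 0.384 × 0.512 = 0.709
- B = 0.512 + 0.384 × 0.896 = 0.856
- C = 0.856 + 0.096 × 0.512 = 0.905
- D = 0.856 + 0.096 = 0.952

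| Assumed p | A | B | B - A = b1² | C | D |
|---|---|---|---|---|---|
| 0.10 | 0.906 | 0.965 | 0.059 | 0.985 | 0.992 |
| 0.20 | 0.709 | 0.856 | 0.147 | 0.905 | 0.952 |
| 0.27 | 0.557 | 0.743 | 0.186 | 0.805 | 0.903 |
| 1/3 | 0.428 | 0.626 | 0.198 | 0.691 | 0.848 |
| 0.50 | 0.172 | 0.313 | 0.141 | 0.359 | 0.688 |

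Every reading of 3.3.2 is more permissive than 8.1 at every rate shown.

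**The case against.** The strongest reply is that the decision is in the past. Section 8.1 records that, before amendment G, "administration of three doses has been determined to be feasible based on the first 20 total patients enrolled", and 8.2 reports 9 of 10 patients meeting that goal by amendment F. Even if 6 of those first 20 patients were at 3.5 mg/kg, 20 - 6 = 14 were at 10 mg/kg, so the first 3-6 at that dose had been passed. An amendment now would govern no remaining escalation decision. This stands, and it limits the consequence to interpretation and reporting.

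Second, the intended rule is easy to infer: one stray clause stands against several consistent statements, and a team running a 3+3 would probably have stopped at 2. That supports calling it a wording error. It does not remove the conflicting threshold from the current text.

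Third, the consequence is real only if exactly 2 DLTs occurred and accrual went on, and nothing in the documents suggests that. With 0 or 1 DLT both rules agree. This is correct, but the count is not reported, so the question stays open until it is.

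Fourth, the probabilities depend on assumed rates and on how 3.3.2 is read. Section 3.7.2 excludes many grade 3 events from the DLT definition, so the true DLT rate may lie well below 27%, and at 10% the gap is about 6 points. This is fair. The conflict itself needs no calculation; the table only shows that the disputed outcome need not be rare.

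**Conclusion.** The concern holds. The 3.3.2 clause contradicts 8.1 at exactly 2 DLTs, and the protocol's own MTD definition shows that 3.3.2 is the one to correct. If 2 of 6 had been accepted, the chance of continuing at 10 mg/kg would rise by 6 to 20 percentage points across assumed true DLT rates of 10% to 50%, under a staged 3+3 in which 2 of the first 3 stops. It would rise by more under looser readings. These sizes rest on assumed rates and on independent patients with a common DLT probability.

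The practical effect is on the safety claim for 10 mg/kg and on the cohorts that depend on it. No sample size, test or efficacy analysis is touched. It should be fixed because it is a stated safety threshold and the correction is nearly free.

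**What to change.** In 3.3.2, change the limit from no more than 2 to fewer than 2, and say that it applies to the first 3-6 patients at 10 mg/kg. The clause then matches 8.1 and 3.7.1.

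In the results, report the number of DLTs and the denominator among those first 3-6 patients, and state which rule was applied when the dose was declared safe. If 2 DLTs occurred and accrual continued, say plainly that 10 mg/kg did not meet the protocol's MTD definition.

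The cost is a one-sentence amendment and a short addition to the results, with no extra patients, data or analyses.
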